#### **Immunology Convention Method:**

If a score at any location/joint is missing, the method described below will be used for deriving mTSS.

- If the score for a location/joint is missing at Baseline, this joint will not contribute to the calculation of mTSS for this subject at any visit within the reading session (even if the score for this location/joint is available at post-baseline visits).

- If the score for a location/joint is missing at all post-baseline visits within a reading session, this joint will not contribute to the calculation of mTSS for this subject at any visit within the reading session (even if the score for this location/joint is available at Baseline).
- If the score for a location/joint is available at Baseline and at least one post-baseline visit, missing scores for this joint at any other post-baseline visit will be imputed assuming no progression from the previous time point with available score.

Sensitivity analysis may be performed as needed.

### **Adjudication process**

Two reviewers will independently review the images. Adjudication will occur for all subjects with pre-specified criteria for that study/indication between the two reviewers' mTSS change scores, in which case another reviewer, different from the reviewers who performed primary assessments, will make a third, independent assessment.

For the calculation of erosion and JSON total score, individual visit score of the 2 closest of the 3 readings (2 primary readers and adjudicator) will be used to determine the final score. If one score is in the middle (equally close), take the middle score. If one of 3 readings is missing, take the average of two non-missing readings. If two of 3 readings are missing, take the non-missing reading. If all 3 readings are missing, erosion/JSON = missing and hence mTSS = missing.

### **No Progression**

No progression of mTSS is defined as a change in mTSS score less than or equal to 0.

## **11.0 Safety Analysis**

### **11.1 General Considerations**

Safety analyses will include reporting of adverse events, laboratory, and vital signs measurements. Safety analyses will be carried out using Safety Analysis Set, which includes all subjects who received at least one dose of study medication in Study M16-244.

Mean changes from baseline in all continuous laboratory parameters and vital signs variables at each visit will be summarized by treatment group. The baseline, minimum, maximum, and final value means will be presented for subjects who have both baseline and post-baseline values. Categorical data will be summarized using frequencies and percentages. Additionally, the number of non-missing values will be given.

### **11.2 Analysis of Adverse Events**

Treatment-emergent adverse events (TEAEs) will be summarized and reported. Frequency of TEAEs will be summarized using subject data from Study M16-244 and a combination of data from Study 1311.5 and Study M16-244 that includes any subject receiving a dose in Study M16-244. Only the combination of data from Study 1311.5 and Study M16-244 that includes any subject receiving a dose in Study M16-244 will be used for per 100 patient years of exposure analyses.

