5.2.2 Exclusion Criteria

A subject will not be eligible for study participation if he/she meets any of the following criteria:

1. Female subject who is pregnant, breastfeeding or is considering becoming pregnant during study participation, including 20 weeks after the last dose of study drug is given.
2. Premature discontinuation of study drug in Study 1311.5 for any reason.
3. Use of a biologic treatment other than risankizumab since first dose of study drug in Study 1311.5.
4. Time elapsed is > 8 weeks since the Week 24 visit in Study 1311.5.
5. Active systemic infections during the last 2 weeks (exception: common cold) prior to randomization, as assessed by the investigator.
6. Anticipated requirement during the study or receipt of any live or attenuated vaccine since first dose administered in Study 1311.5.
7. Participation in another investigational study since first dose of study drug in Study 1311.5.
8. Current diagnosis of a major chronic inflammatory or connective tissue disease other than PsA (e.g., rheumatoid arthritis, systemic lupus erythematosus, ankylosing spondylitis, Lyme disease, gout) and fibromyalgia as assessed by the Investigator.
9. Use of any restricted medication as specified in this protocol or any drug considered likely to interfere with the safe conduct of the study, as assessed by the investigator, since first dose of study drug in Study 1311.5.
10. History of allergy/hypersensitivity to a systemically administered biologic agent or its excipients.
11. Chronic or relevant acute infections including HIV (human immunodeficiency virus), viral hepatitis and (or) active tuberculosis.
12. Any documented active or suspected malignancy or history of malignancy since first dose of study drug in Study 1311.5, except appropriately treated basal or squamous cell carcinoma of the skin or in situ carcinoma of uterine cervix.

13. Major surgery (including weight loss surgery), performed since first dose of study drug in Study 1311.5 or planned while study is ongoing as assessed by the investigator.

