## **9.0 Study Drug Exposure and Compliance**

A summary of study drug duration will be provided for the Safety Analysis Set.

Study drug duration (days) will be summarized with the number of subjects, mean, standard deviation, minimum, median and maximum for each treatment arm. It will also be summarized in 4-week intervals with frequencies and percentages for the number of subjects receiving study drug doses in each interval. In addition cumulative duration of risankizumab (including total subject years) will be summarized.

The study drug duration will be calculated as follows:

Duration = date of last injection – date of first injection + 84 day

Total drug duration across Study 1311.5 (feeder) and Study M16-244 (OLE) will be calculated as follows:

Duration over both studies = date of last injection in Study M16-244 – date of first injection in Study 1311.5 + 84 day – MAX(0, date of first injection in Study M16-244 – date of last injection in Study 1311.5 – 84)

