#### 9. Adverse Event per 100 Patient Years of Exposure in Study 1311.5 and Study M16-244

The treatment-emergent adverse events occurring during Study 1311.5 and Study M16-244 will be presented by event rate per 100 patient year. These will be

---

presented for any TEAEs, serious adverse events, AE of special interest in addition to MACE events.

AEs per 100 patient years of exposure is defined as the number of AEs divided by the total exposure in 100 patient years. Note that one event per preferred term per day per subject will be counted in the calculation of the number of AEs (i.e., a preferred term will not be counted twice on the same day for the same subject). See the calculation method below.

$$100 \times \frac{\text{Number of TEAEs}}{\text{Total Patient Years}}$$

where total patient years is defined as the sum of the study drug exposure (defined in Section 9.0) of all subjects normalized by 365.25, and rounded to one decimal place.

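### The only planned adverse-event rates per 100 patient-years include Study 1311.5 time that, under the entry rules, cannot contain deaths, drug-stopping events or non-exempt malignancies, so rates for those events are diluted

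*SAP*

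**What the plan says.** SAP 11.1 fixes the population as those dosed in the extension: "Safety analyses will be carried out using Safety Analysis Set, which includes all subjects who received at least one dose of study medication in Study" (the study meant is M16-244). SAP 11.2 then plans treatment-emergent event frequencies in two ways, from M16-244 alone and from "a combination of data from Study 1311.5 and Study M16-244 that includes any subject receiving a dose in Study M16-244". For rates per 100 patient-years it allows only the second: "Only the combination of data from Study 1311.5 and Study M16-244 that includes any subject receiving a dose in Study M16-244 will be used".

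Item 9 of SAP 11.2.1 says the rates are "presented for any TEAEs, serious adverse events, AE of special interest in addition to MACE events". The denominator is given there as "where total patient years is defined as the sum of the study drug exposure (defined in Section 9.0) of all subjects", converted to years by 365.25. SAP 9.0 defines an M16-244-only duration and a two-study duration, the latter being "Duration over both studies = date of last injection in Study M16-244 – date of first injection in Study 1311.5 + 84 day", less any part of the interval between the last feeder injection and the first M16-244 injection that exceeds 84 days. SAP 11.2.1 counts events as treatment-emergent until 140 days after the last dose.

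On entry, Protocol 5.2.1 (criterion 1) requires all Study 1311.5 doses and its Week 24 visit. Protocol 5.2.2 excludes "Premature discontinuation of study drug in Study 1311.5 for any reason" (criterion 2). It also excludes "Any documented active or suspected malignancy or history of malignancy since first dose of study drug in Study 1311.5" (criterion 12), apart from treated basal or squamous skin cancer and in situ cervical carcinoma.

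**The concern.** Membership of the pooled set is decided by something that happens later, an M16-244 dose, yet each member's clock runs back to the first feeder injection. Anyone who died, stopped drug or developed a non-exempt malignancy in Study 1311.5 is missing from the set, while the feeder time of everyone else stays in the denominator. For those events the feeder period adds days but no cases. This is guarantee-time bias, and it lowers the rate.

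It matters because safety is the primary objective and no M16-244-only rate is planned. The M16-244-only results are percentages of subjects. A reader would naturally take the pooled rates as on-drug rates, and nothing in the SAP says they are conditional on having completed the feeder study.

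**Working it through.** The documents give no expected event rate and no rate calculation, so there is no planned figure to reproduce. The check applies the SAP 9.0 duration formulas directly.

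**Inputs from the documents**
- M16-244 doses at Weeks 0, 12, 24 and 36 (Protocol 5.1), so a completer's last dose falls 252 days after the first.
- Feeder Week 24 visit at day 168. M16-244 may start the same day or up to 8 weeks (56 days) later (Protocol 5.1, 5.2.2).
- Exposure credit of 84 days after the last injection (SAP 9.0). Event window of 140 days after the last dose (SAP 11.2.1).

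**Assumptions**
- The date of the last feeder injection is not given. Protocol 5.6.4 says only that 150 mg is given every 4 to 12 weeks and 75 mg as a single dose. I tried Weeks 0, 12, 16 and 20.
- The hazard is constant.
- Item 9 uses the two-study duration. It does not say which duration it means, but SAP 11.2 implies this one.

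**Feeder share for an M16-244 completer**
- M16-244 exposure: 252 + 84 = 336 days.
- Same-day rollover, last feeder injection at Week 12 or later: pooled exposure = (168 + 252) + 84 − 0 = 504 days. Feeder share = (504 − 336)/504 = 168/504 = 33%.
- Last feeder injection at Week 0: the deduction is 168 − 0 − 84 = 84 days, so pooled exposure = 420 days. Share = 84/420 = 20%.
- Last feeder injection at Week 20 with an 8-week gap: pooled exposure = (224 + 252) + 84 − 0 = 560 days. Share = 224/560 = 40%.
- At the ceiling of 180 subjects, all completing on the 504-day pattern: 180 × 168/365.25 = 82.8 of 180 × 504/365.25 = 248.4 patient-years.

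**Reported rate over true rate, for an event that bars entry**

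The ratio is the number of days on which the event can be counted, divided by pooled exposure days.
- SAP windows: (252 + 140)/504 = 392/504 = 0.78. Range for completers: 392/560 = 0.70 to 392/420 = 0.93.
- Events and exposure both ending 84 days after the last dose: 336/504 = 0.67.
- A true rate of 1.0 per 100 patient-years would thus be reported as 0.67 to 0.78 on the 504-day pattern.

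**Early leavers** (same-day rollover, last feeder injection at Week 12 or later)
- Last M16-244 dose at Week 12: share 168/336 = 50%, ratio (84 + 140)/336 = 0.67.
- One M16-244 dose only: share 168/252 = 67%, ratio 140/252 = 0.56.

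**Placebo time.** The SAP does not say whether placebo subjects' feeder time enters the denominator. If 10% to 33% of subjects had placebo (assumed) and that time were left out, feeder days per subject average 151.2 to 112.6. The share is then 151.2/487.2 = 31% to 112.6/448.6 = 25%, and the ratio 392/487.2 = 0.80 to 392/448.6 = 0.87.

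The ratio was below 1 in every scenario tried.

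**The case against.** The strongest reply is that the pooled population matches the stated objective, which concerns subjects who completed Study 1311.5. M16-244-only frequencies and listings of deaths and serious events are planned, and nothing is tested. That stands as far as it goes: the defect lies in what the rates mean, not in a test result. But percentages are not rates, and matching the objective does not make feeder time able to contain events that the entry rules remove.

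A reader might infer more than the documents support:
- **A flat one-third understatement.** This gives events and exposure the same 84-day tail. The SAP counts events for 140 days but credits 84, which pushes rates up and partly offsets the selection. The one-third share also depends on feeder dates that are not given.
- **All the reported rates include event-free time.** Ordinary events, and non-fatal serious events or MACE that did not stop dosing, can occur and be counted in feeder time. Deaths and discontinuations have no rate table named in item 9. Deaths reach the rates as fatal serious events and as cardiovascular death within MACE.
- **Any feeder infection or laboratory finding bars entry.** Exclusion 11 has no wording that reaches back to the first feeder dose, so a resolved infection is not barred by its text. Exclusion 14 requires the investigator to judge a finding both clinically significant and disqualifying.
- **Malignancy certainly has its own rate.** Item 9 refers to events of special interest. In the protocol that means hepatic injury, while malignancy is an area of safety interest in SAP Table 14. The SAP does not say which list applies.
- **The events are strictly impossible.** SAP 7.4 allows for subjects who entered without meeting the criteria.

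**Conclusion.** The concern holds in limited form. The rates per 100 patient-years rest on feeder person-time that, barring entry deviations, cannot contain deaths, drug-stopping events or non-exempt malignancies. For such an event the reported rate is about 0.78 of the true rate for an M16-244 completer, with a range of 0.70 to 0.93, and lower for early leavers. The direction is clear. The size rests on a constant hazard, on assumed feeder injection dates and gaps, on feeder time being counted for all entrants, and on item 9 using the two-study duration. Totals for serious events and MACE are diluted only through the part of them that bars entry. The documents do not allow that part to be quantified.

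**What to change.** In SAP 11.2 and item 9 of SAP 11.2.1:
- Remove the restriction of rates to the pooled data, and add M16-244-only rates for serious events, events of special or safety interest (stating which list applies) and MACE.
- Count events and person-time in these rates from the first M16-244 dose over the same post-dose window, for example both to 140 days after the last dose or end of follow-up. Using the 84-day credit against 140-day events would overstate the rate: 392/336 = 1.17. Matched windows give 392/392 = 1.00.
- Keep the pooled rate, state which SAP 9.0 duration it uses, and label it as conditional on completing Study 1311.5 and entering M16-244. Do not use it as the on-drug rate for deaths or malignancies.
- Add risankizumab subjects who did not roll over only if their data are available. Another company sponsored Study 1311.5, and the SAP draws on its event data only for subjects dosed in M16-244.

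The cost is SAP wording and one extra set of tables, with no change to trial conduct. The M16-244-only rates carry less person-time. A completer contributes one third less with the 84-day credit (336 against 504 days), or 22% less if 140 days are credited (1 − 392/504). Rates for the affected events are likely to look less favourable.

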#### **11.2.1 Treatment-Emergent Adverse Events**

All adverse events occurring between start of treatment and end of the residual effect period (REP) will be considered 'treatment emergent.' The REP is defined as 20 weeks (140 days) after the last trial medication application and will include adverse events reported through EOS visit. Adverse events that start before first drug intake and deteriorate under treatment will also be considered as 'treatment-emergent.'

Events where the onset date is the same as the study drug start date are assumed to be treatment emergent, unless the study drug start time and the adverse event start time are

collected and the adverse event start time is prior to the study drug start time. If an incomplete onset date is collected for an adverse event, the event will be assumed to be treatment-emergent unless there is other evidence that confirms that the event is not treatment-emergent (e.g., the event end date is prior to the study drug start date).

Adverse events that occur outside of 140 days from last dose in Study 1311.5 but before first dose in Study M16-244 will not be considered treatment emergent.

The number and percent of subjects experiencing treatment-emergent TEAEs will be tabulated using the Medical Dictionary for Drug Regulatory Activities (MedDRA®) version 20.0 by system organ class (SOC) and preferred term (PT).

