## 11. Listing of Adverse Events

The following additional summaries of AEs will be prepared.

- Listing of Subjects with TEAE of Area of Safety Interests
- Listing of Subjects with Pretreatment Serious Adverse Events
- Listing of Subjects with Treatment-Emergent Serious Adverse Events
- Listing of all adverse events that led to discontinuation of study drug

- Listing of all deaths

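### The per-100-patient-year adverse event rates count events to 140 days after the last dose but person-time to only 84 days

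*SAP*

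**What the plan says.** **Which rates.** SAP 11.2 says "Only the combination of data from Study 1311.5 and Study M16-244 that includes any subject receiving a dose in Study M16-244 will be used for" analyses per 100 patient-years. Item 9 of SAP 11.2.1 applies them to any treatment-emergent event, serious events, events of special interest and MACE. M16-244 data alone are summarised as numbers and percentages of subjects.

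**Numerator.** SAP 11.2.1: "The REP is defined as 20 weeks (140 days) after the last trial medication application and will include adverse events reported through EOS visit". For the period between studies: "Adverse events that occur outside of 140 days from last dose in Study 1311.5 but before first dose in Study M16-244 will not be considered" treatment-emergent. Gap events therefore count up to 140 days after the last Study 1311.5 dose.

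**Denominator.** Item 9: "where total patient years is defined as the sum of the study drug exposure (defined in Section 9.0) of all subjects", converted to years. In SAP 9.0 the M16-244 formula is "Duration = date of last injection – date of first injection + 84 day". The pooled formula is "Duration over both studies = date of last injection in Study M16-244 – date of first injection in Study 1311.5 + 84 day", minus the following quantity when it is positive: "date of first injection in Study M16-244 – date of last injection in Study 1311.5 – 84". Gap time beyond 84 days is therefore dropped.

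**Protocol.** Sections 6.1.4 and 8.1.6.2.1 agree with the 140-day event limit. Section 5.1 sets an end-of-study visit at 16 weeks and a phone call at 20 weeks after the last dose. Appendix U limits the call to subjects who signed the Amendment 1 consent. The protocol plans no rate per patient-year.

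**The concern.** A rate estimates risk per unit time only if its events arise in the time that is counted. Here up to 56 days per subject (140 − 84) can contribute events but no person-time, and nothing in either document limits the rate numerator to the 84-day period.

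These are the only exposure-adjusted rates planned in a study whose primary objective is safety. They are the figures a reader would set beside rates from other risankizumab studies. The mismatch also depends on when subjects stop and how long they are followed. Two cohorts with the same true risk but different dropout would report different rates.

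**Working it through.** The documents state no adverse event rate and no patient-year total, so there is no plan figure to reproduce. The check applies the SAP formulas to individual subject histories.

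**Inputs**
- First Study 1311.5 injection to a same-day roll-over at Week 24: 169 − 1 = 168 days (target day in SAP Table 5).
- First to last extension injection, O: 252, 168, 84 or 0 days for 4, 3, 2 or 1 scheduled 12-weekly doses (Protocol 5.1).
- Exposure credited after the last injection: 84 days (SAP 9.0).
- Event capture after the last dose, F: 112 days (16-week visit) or 140 days (20-week call).
- Assumptions: constant risk, and no gap between studies beyond 84 days.

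**Formulas**
- Counted person-time = 168 + O + 84
- Event window = 168 + O + F
- Inflation = event window / counted person-time

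| Extension doses | Counted days | Window, F = 112 | Ratio | Window, F = 140 | Ratio |
|---|---|---|---|---|---|
| 4 | 504 | 532 | 1.06 | 560 | 1.11 |
| 3 | 420 | 448 | 1.07 | 476 | 1.13 |
| 2 | 336 | 364 | 1.08 | 392 | 1.17 |
| 1 | 252 | 280 | 1.11 | 308 | 1.22 |

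The excess stays at 28 or 56 days while the denominator shrinks, so the ratio rises with early stopping, provided the subject is still followed.

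**Subjects lost early.** SAP 9.0 credits 84 days after the last injection whether or not the subject is seen. With one extension dose and last contact 30 days later, observed time is 168 + 30 = 198 days against 252 counted. The ratio is 198/252 = 0.79, so the rate is too low. It crosses 1 when last contact falls 84 days after the last dose.

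**Gap between studies.** Let S be the days from first Study 1311.5 injection to first extension injection, and L the day of the last Study 1311.5 injection.
- Counted = S + O + 84 − max(0, S − L − 84)
- Window = S + O + F − max(0, S − L − 140)

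The documents do not give L, so these completer cases (O = 252, F = 140) are assumptions:
- L = 140 with the full 8-week delay (S = 224): 616/560 = 1.10.
- L = 112 with the same delay: counted 560 − 28 = 532; 616/532 = 1.16.
- L = 0 with no delay (S = 168): counted 504 − 84 = 420; window 560 − 28 = 532; 532/420 = 1.27. Protocol 5.6.4 describes a single-dose regimen in Study 1311.5 but does not say whether dummy injections followed.

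**M16-244 alone.** On the +84-day duration, a completer's rate would be too high by (252 + 112)/(252 + 84) = 364/336 = 1.08, to (252 + 140)/336 = 392/336 = 1.17.

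**The case against.** **Size and direction.** A reader might take 6% to 11% as the bias in the reported rate, or conclude that the rate is always too high. The documents support neither. The range needs constant risk through day 140, but after day 84 a completer has one visit and one call, and the call covers only Amendment 1 signers. Lower ascertainment there would shrink the effect. Protocol 5.4.1 provides for loss to follow-up and refusal of contact, where the bias can reverse. Between-study gaps could push it above 11%. This objection stands, and the figures are stated as conditional for that reason.

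**Materiality.** The rates are descriptive and untested. With an assumed 20 serious events, an exact Poisson 95% interval is 12.2 to 30.9, or −39% to +54%, far wider than 6% to 11%. That limits the importance for rare events. It does not remove a systematic error that more data would not reduce, and any-event rates rest on larger counts.

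**The 84-day convention.** It is one dosing interval, which is sensible for an exposure table. It does not justify dividing 140-day events by 84-day time.

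**Pooling.** A reader might also infer that omitting an M16-244-only rate is an error, or that completer-only Study 1311.5 time materially dilutes the rates. The first is an explicit, pre-specified choice. Crude rates for serious events could be rebuilt from the planned "Listing of Subjects with Treatment-Emergent Serious Adverse Events" and the M16-244 duration, though with the +84-day problem. For the second, SAP 11.2 openly defines the pooled set as subjects dosed in M16-244. Entry required completing Study 1311.5 dosing, so some dilution for fatal or treatment-ending events is plausible, but the documents give no means of sizing it. That leaves a labelling point.

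**Conclusion.** The mismatch is explicit in the SAP, no other section cures it, and it should be fixed before analysis. For a direct-rollover completer followed to the 16-week visit or the 20-week call, the pooled rate is inflated by a factor of 1.06 to 1.11. This assumes constant risk and no between-study gap beyond 84 days. It is an illustration for one type of subject and neither a floor nor a ceiling. For the cohort, the net size and even the sign depend on dropout, completeness of follow-up and the Study 1311.5 injection dates, none of which the documents give. The consequence is a rate whose bias is uncontrolled and differs between cohorts with different follow-up. The M16-244 tables of numbers and percentages are not touched.

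**What to change.** In SAP 9.0 and SAP 11.2.1 item 9:

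1. For every rate per 100 patient-years, run person-time from first dose to the earlier of last dose + 140 days or last contact. In the between-study gap, drop only time beyond 140 days after the last Study 1311.5 injection. Count events over exactly that interval. Keep +84 days for the exposure table only.
2. State whether prior-placebo time in Study 1311.5 is in or out, and apply the same rule to events and person-time. The pooled duration starts at the first Study 1311.5 injection, and item 9 is silent on placebo time. If the rate is meant as a risankizumab rate, start both at the first risankizumab dose.
3. Optional and cheap: add an M16-244-only rate from the first extension dose on the same matched person-time, and label the pooled rate as describing a rollover population. Adding that rate on the +84-day duration would carry a larger mismatch than the pooled rate does.

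**Cost.** SAP wording and a little programming, with no new data and no change to the Safety Analysis Set. Under step 1 alone, a completer's stated pooled rate falls by about 5% to 10% (504/532 = 0.95; 504/560 = 0.90). The effect of removing placebo time cannot be computed, because the documents do not give the number of prior-placebo subjects.
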